14.3.9.2 Vital signs

The change in vital signs (blood pressure, pulse, body temperature) from baseline to each visit will be summarised as mean, standard deviation, median, minimum, and maximum values for each treatment group.

14.3.9.3 Clinical laboratory evaluation

The change in each of the laboratory parameters from baseline to each visit will be summarised by visit and treatment group as mean, standard deviation, median, minimum, and maximum values.

Laboratory parameters will be classified as 'low', 'normal' or 'high', depending on whether the value is below, within or above the reference range, respectively. A shift table will be produced showing the categories at baseline against those at end of treatment. Subjects with laboratory parameters outside the reference range will be listed.

14.3.9.4 Subject assessment of local tolerability

Subject assessment of local tolerability will be summarised by visit and treatment group.

14.3.10 Pharmacokinetics

A separate report will be written by the respective bioanalytical CRO and added as an addendum to the CTR.

Plasma concentrations of delgocitinib will be listed and plotted versus time since last IMP application by treatment group.

14.3.11 Interim analysis

No interim analysis is planned.

14.3.12 General principles

Unless otherwise stated, all significance tests will be 2-sided using the 5% significance level. All CIs will be presented with 95% degree of confidence.

An observed-cases approach will be used for tabulations of data by visit (i.e., involving only those subjects who attended each specific visit).

Categorical data will be summarised using the number and percentage of subjects in each category and treatment group. Continuous data will be summarised using the mean, median, standard deviation, minimum, and maximum values.

All the analyses specified in the protocol will be reviewed in relation to the blinded data actually obtained and the statistical analysis plan will be finalised before breaking the randomisation code.

Any changes from the statistical analysis planned in this clinical trial protocol will be described and justified in a protocol amendment, the statistical analysis plan and/or in the CTR dependent on the type of deviation.

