Early termination: subjects, who discontinue IMP treatment prior to Week 16 or withdraw from trial will be asked to return to the trial site for end of treatment assessments at an

early termination visit as soon as possible after the last IMP application for completion of all trial procedures scheduled for the visit at Week 16 (except for the skin biopsy, if the subject has consented to have skin biopsies obtained). They will also be asked to return at Week 16 (see footnote 5).

- 4) All subjects will be asked to return to the trial site approximately 2 weeks after the last IMP application for assessment of safety at a follow-up visit.
- 5) Subjects who discontinue IMP treatment prior to Week 16 will be asked to return to the trial site at Week 16 for a primary endpoint visit.
- 6) Unscheduled visits may occur if subjects need to make a visit in between the scheduled visit dates due to an AE, difficulty complying with the trial protocol requirements, or a significant change in their disease state.
- 7) The informed consent form must be signed prior to performing any protocol-related procedures, including but not limited to screening evaluations and alteration of ongoing treatments unless medically justified.
- 8) All returned IMP tubes will be weighed by the CMO.
- 9) Relevant prior/concomitant medication should be included from 6 months prior to Day 1 (baseline) until end of trial.
- 10) Relevant medical history must be recorded from the subject's date of birth. In case medical history is incomplete at screening visit, missing data will be retrieved at Day 1 (baseline).
- 11) Completion of the eDiary will be initiated at the latest 1 week prior to Day 1 (baseline).
- 12) Only for subjects with a paid job.
- 13) Subjects do not have to be fasting for safety laboratory samples.
- 14) Subjects with high risk of latent tuberculosis (e.g. prior residence in or travel to countries with high prevalence of tuberculosis, close contact with a person with active tuberculosis, or a history of active or latent tuberculosis where an adequate course of treatment cannot be confirmed) must be tested.
- 15) For women of childbearing potential, a serum pregnancy test must be performed at the screening visit, and a urine pregnancy test at Day 1 (baseline), Weeks 4, 8, 12, and 16 (end of treatment).
- 16) If a subject reports an AE, it is up to the investigator's discretion to perform an unscheduled visit.

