5.3 Trial rationale

The purpose of this phase 2b trial is to establish a dose-response signal and to evaluate the efficacy and safety of delgocitinib (1, 3, 8, and 20 mg/g), formulated as a cream for topical use, in the treatment of subjects with mild to severe chronic hand eczema. The results from this trial will support further development in phase 3 with regards to e.g., dose selection and treatment duration.

There is a clear unmet need for new treatment options in the treatment of patients suffering from chronic hand eczema. Based on currently available non-clinical and clinical data, delgocitinib has the potential to become a novel local-acting anti-inflammatory and immunosuppressive agent with skin barrier improving properties (10) for topical use in chronic hand eczema. There is a reasonable expectation that delgocitinib in a cream formulation will prove to be an effective and well-tolerated treatment based on the mechanism of action, and thereby facilitate the everyday lives of affected patients.

CCI

CCI

[figure not shown]

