10.3 Early termination assessments

An end of trial form must be completed for all subjects, including subjects who withdraw from the trial or discontinue IMP treatment, at their last trial visit (the early termination visit, the safety follow-up visit, or the primary endpoint visit, whichever comes last).

Withdrawal from trial

Subjects, who withdraw from the trial must attend an early termination visit as soon as possible after last administration of IMP (see the schedule of trial procedures [Section 4] for data to be collected at an early termination visit). The investigator will review any AEs which will be followed-up according to Section 13.7, if the subject agrees.

Discontinuation of IMP

Subjects, who discontinue IMP prior to Week 16 will be asked to attend an early termination visit as soon as possible after last IMP application and return to the trial site for 2 additional visits as indicated below. See the schedule of trial procedures (Section 4) for data to be collected at these visits.

Subjects, who discontinue IMP prior to Week 16 will be asked to attend:

- Early termination visit (as soon as possible after the last IMP application).
- Safety follow-up visit (2 weeks after the last IMP application).
- Primary endpoint visit (16 weeks after the first IMP application).

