14.3.5 Analysis of primary efficacy endpoint

The primary endpoint IGA TS at Week 16 will be analysed for the full analysis set and for the per protocol analysis set. The per protocol analysis is regarded as supportive.

IGA TS refers to IGA score of 0 (clear) or 1 (almost clear) with ≥ 2 -step improvement from baseline.

For the analysis of the primary endpoint, subjects who initiate rescue medication before Week 16 or withdraw from the trial and have no retrieved data at Week 16, will all be considered non-responders.

The Multiple Comparison Procedure – Modelling (MCP-Mod) approach (see e.g., EMA Qualification Opinion of MCP-Mod [23] or Bretz et al [24] for further details of the framework) will be used to guide dose selection. The dose-response relationship for the binary endpoint IGA TS will be modelled by the following 3 identified candidate models. These candidate models are selected based on the expected dose-response.

Linear in log: $E_0 + \delta \times \log(d + c)$,

E_{max} : $E_0 + E_{max} \times d / (ED_{50} + d)$,

Sigmoid E_{max} : $E_0 + E_{max} \times d^h / (ED_{50}^h + d^h)$,

where d is the dose (incl. vehicle), E_0 is the efficacy offset (anticipated vehicle effect), E_{max} is the asymptotic maximum effect, ED_{50} is the half-life value of E_{max} , h is the steepness at ED_{50} , δ is the slope parameter, and c is a fixed offset parameter.

The models will be adjusted for the stratification variables region and baseline IGA. The model parameters (ED_{50} , h) will be prespecified a priori by suitable guesses based on data from Japan Tobacco's dose-ranging trial QBA2-1 (25). Akaike's Information Criteria will be

used as the goodness-of-fit criterion that will drive the selection of the dose-response model that fits data best while controlling the family-wise error rate at 5%. Based on the selected model, the dose-response relationship will be estimated and presented with 2-sided 95% CI. If none of the candidate models converge, other possibilities of models and goodness-of-fit criteria will be explored. The dose-response modelling will be performed on both the total population and subjects having a baseline IGA of 3 or 4, in order to further explore heterogeneity in the disease population.

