14.3.7.2 Efficacy over time

To further explore possible early onset of effect and general efficacy over time, the following endpoints will be evaluated at each scheduled assessment up to Week 14 or each week up to Week 15:

- IGA TS at each scheduled assessment until Week 14.
- PaGA TS at each scheduled assessment until Week 14.
- Change from baseline to each week through Week 1 to 15 in HESD NRS (weekly average for each individual symptom).
 - Reduction of worst pruritus (weekly average) – one of the symptoms captured in the HESD – of at least 4 from baseline to each week through Week 1 to 15 among subjects with baseline worst pruritus (weekly average) of at least 4.
- Change from baseline to each scheduled assessment until Week 14 in HEIS (for each individual item).
- Change in DLQI score from baseline to each scheduled assessment until Week 14.
- Reduction of DLQI of at least 4 from baseline to each scheduled assessment until Week 14.

For the binary endpoints, the same Cochran-Mantel-Haenszel test as for the Week 16 assessment will be applied. For the continuous endpoints, the repeated measurements model already described previously for the Week 16 assessments facilitates that the p-values, treatment differences and 95% CIs can be derived for each visit up to Week 14 (or Week 15 for the change in HESD NRS (weekly average)).

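### By-visit responder rates use observed cases although subjects who stop IMP leave the visit schedule until Week 16, so the rates are probably too high and not comparable with the primary Week 16 result

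*Combined protocol and SAP*

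**What the plan says.** The general principles (Section 14.3.12) set the rule for tables: "An observed-cases approach will be used for tabulations of data by visit (i.e., involving only those subjects who attended each specific visit".

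Section 10.3 describes what is asked of a subject who stops IMP before Week 16. The subject attends an early termination visit and is asked to "return to the trial site for 2 additional visits as indicated below": a safety follow-up two weeks after the last application, and a "Primary endpoint visit (16 weeks after the first IMP application"). Footnote 3 to Panel 2 (Section 4) makes the early termination visit a full assessment, "for completion of all trial procedures scheduled for the visit at Week 16", biopsy excepted. Footnote 5 confirms that these subjects "will be asked to return to the trial site at Week 16 for a primary endpoint visit". Nothing asks them to attend the other scheduled visits in between. Under Sections 9.5 and 10.2.1, starting rescue treatment ends IMP for good, so every rescued subject follows this reduced schedule.

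Section 14.3.7.2 lists responder endpoints over time: IGA TS, PaGA TS and the DLQI response at each scheduled assessment to Week 14, and the pruritus response weekly to Week 15. On method it says: "For the binary endpoints, the same Cochran-Mantel-Haenszel test as for the Week 16 assessment will be applied". Section 14.3.13 says that missing-value procedures are given in the section for each analysis, but Section 14.3.7.2 gives none.

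The non-responder rule is in Section 14.3.5 and is worded for the primary endpoint. Subjects who start rescue before Week 16, or who "withdraw from the trial and have no retrieved data at Week 16, will all be considered non-responders".

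**The concern.** Absence from the by-visit tables is built into the schedule and is likely to be informative. Rescue is for symptoms the subject cannot tolerate, and lack of efficacy is one of the recorded reasons for stopping (Section 10.1). A treatment failure can thus be missing from the Week 14 denominator and yet count as a failure in the Week 16 primary result. A reader who joins the by-visit rates to that result sees one curve made from two populations under two rules.

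This matters because Section 5.3 says the trial is to inform phase 3 on "dose selection and treatment duration", and Section 14.3.7.2 presents these endpoints as the evidence on early onset and efficacy over time. What is at stake is the reading of the time course. The primary conclusion is not.

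**Working it through.** **Inputs.** Response rates of 45% (active) and 15% (vehicle), 50 subjects per arm, two-sided 5%: Section 14.1. Visits asked of IMP stoppers: Sections 4 and 10.3. Table rule: Section 14.3.12. Primary rule: Section 14.3.5. The plan gives no IMP stopping rate, no return rate and no response rate after stopping. Those values are assumptions, shown as ranges.

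**Step 1: the plan's own figure.** Power for 45% against 15% with 50 per arm, pooled normal approximation:
- SE under the null = √(2 × 0.30 × 0.70 / 50) = 0.0917
- SE under the alternative = √((0.45 × 0.55 + 0.15 × 0.85) / 50) = 0.0866
- Power = Φ((0.30 − 1.96 × 0.0917) / 0.0866) = 91.8%

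This agrees with the stated power of just over 90%. The point does not depend on it; it only confirms the rates used below.

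**Step 2: who is counted where.**

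| Subject | Table at visits between stopping and Week 14 | By-visit CMH test | Week 16 primary analysis |
|---|---|---|---|
| Starts rescue | Not in denominator | Not stated | Non-responder |
| Withdraws, no Week 16 data | Not in denominator | Not stated | Non-responder |
| Stops IMP without rescue, returns at Week 16 | Not in denominator | Not stated | Observed result |

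The pruritus response comes from diary weeks, so visit attendance is not its literal criterion. It equally lacks a rule for missing weeks.

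**Step 3: effect on a tabulated rate.** Let m be the share absent, and assume every absent subject is a non-responder. Shown rate = true rate / (1 − m).

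| m | True 45% shown as | True 15% shown as |
|---|---|---|
| 5% | 0.45/0.95 = 47.4% | 0.15/0.95 = 15.8% |
| 10% | 0.45/0.90 = 50.0% | 0.15/0.90 = 16.7% |
| 20% | 0.45/0.80 = 56.3% | 0.15/0.80 = 18.8% |
| 25% | 0.45/0.75 = 60.0% | 0.15/0.75 = 20.0% |

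**Step 4: effect on the difference between arms (true value 30 points).**
- 20% absent in both arms: 56.25 − 18.75 = 37.5 points.
- 10% absent on active, 30% on vehicle: 50.0 − 0.15/0.70 = 50.0 − 21.4 = 28.6 points.

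The difference can grow or shrink.

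**Step 5: step from Week 14 to Week 16 within an observed-case table.** Let r be the rate among subjects still on schedule, d the share stopped, f the share of stoppers who return, and q the response rate of returners. Week 16 rate = [r(1 − d) + f·d·q] / [(1 − d) + f·d]. With d = 20%:

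| r | f | q | Week 16 rate | Step (points) |
|---|---|---|---|---|
| 45% | 1 | 0% | 0.36/1.00 = 36% | −9 |
| 45% | 0.5 | 0% | 0.36/0.90 = 40% | −5 |
| 45% | 0 | – | 0.36/0.80 = 45% | 0 |
| 45% | 1 | 45% | (0.36 + 0.09)/1.00 = 45% | 0 |
| 45% | 1 | 60% | (0.36 + 0.12)/1.00 = 48% | +3 |
| 15% | 1 | 45% | (0.12 + 0.09)/1.00 = 21% | +6 |

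If an observed-case 45% at Week 14 is instead set beside the primary rule, and all stoppers have withdrawn without data, Week 16 is 0.45 × 0.80 = 36%.

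**Step 6: check on the remedy.** Suppose missing visits are counted as non-response up to Week 14 while Week 16 keeps the primary rule. With r = 45%, d = 20%, and all stoppers returning unrescued with 45% response, Week 14 is 0.45 × 0.80 = 36% and Week 16 is 0.36 + 0.20 × 0.45 = 45%. That is a 9-point artificial rise, so Week 16 also has to be shown under the by-visit rule.

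**The case against.** The best defence is that the observed-cases sentence governs tables only, and that applying the same CMH test as at Week 16 carries the primary non-responder rule to earlier visits. The first half stands: the documents do not say that the tests use observed cases, and a reader who infers this goes too far. The second half does not close the gap. The primary rule covers rescue, or withdrawal without Week 16 data. A subject who stops without rescue and returns at Week 16 meets neither condition and has no assessment in between. The tables omit all absent stoppers on either reading.

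A reader might also infer that stoppers skip every visit until Week 16. They do not: the early termination visit includes the efficacy assessments. The gap is that the plan does not say to which nominal visit those data belong.

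Nor do the documents support an unconditional fall at Week 16. Step 5 gives falls, no change and rises. Upward bias is likely if stoppers respond less often than those who stay, but it is not certain, because an unrescued stopper may be a responder. Absence also accumulates, so the effect is weakest at the first visits.

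Finally, these are other endpoints. Time to IGA TS (Kaplan-Meier) and HECSI (MMRM estimates at each visit) also describe the time course, and neither is an observed-case table. That limits the weight of the point. The deferral to the SAP in Sections 14.3.5 and 14.3.6 concerns sensitivity analyses of the primary and secondary endpoints, not these endpoints.

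**Conclusion.** The point holds in a limited form. A stated observed-cases table rule, combined with a schedule that takes IMP stoppers off the remaining visits, makes by-visit responder rates probably too high and not comparable with the primary Week 16 result. Separately, handling of missing data in the by-visit CMH tests is unspecified.

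The size is illustrative only: about 2 to 15 points on a 45% rate and 1 to 5 points on a 15% rate, if 5% to 25% are absent and none of them responds. The direction of any effect on the treatment difference, and of any step at Week 16, cannot be fixed from the documents. The primary Week 16 analysis and the MMRM analyses are unaffected.

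**What to change.** In Sections 14.3.7.2 and 14.3.12, or in the SAP before the code is broken:

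1. State that tables and CMH tests of binary efficacy endpoints at each visit use all full analysis set subjects (for the pruritus and DLQI responses, all those meeting the baseline threshold). Count a subject as a non-responder after rescue, or when there is no assessment at that visit.
2. State how early termination data map to nominal visits, and show the number assessed per visit and arm.
3. In the time-course display, show Week 16 with IMP stoppers handled as at earlier visits, next to the primary-rule Week 16 result, so that the curve follows one rule throughout.
4. Keep observed-case figures as a secondary display. This also shows how far isolated missed visits, counted as failures under item 1, pull the rates down.

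The cost is SAP wording, one more set of tables, and slightly less favourable by-visit rates. No data collection and no primary analysis changes.

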Appendix 1: Definitions of adverse events and serious adverse events

Adverse event definition

An AE is defined as any untoward medical occurrence in a patient or clinical investigation subject administered a pharmaceutical product and which does not necessarily have a causal relationship with this treatment. An AE can therefore be any unfavourable and unintended sign (including an abnormal laboratory finding), symptom, or disease temporally associated with the use of a medicinal (investigational) product, whether or not related to the medicinal (investigational) product. (ICH Harmonized Tripartite Guideline for Good Clinical Practice, E6 (R1)).

This definition includes:

- Accidental injuries.
- Events related to trial procedures.
- Reasons for any unfavourable and unplanned change in medication (drug and/or dose).
- Clinically significant worsening of pre-existing conditions.
- Reasons for admission to hospital or surgical procedures unless these were planned before the subject consented to trial participation.
- AEs commonly observed, and AEs anticipated based on the pharmacological effect of the IMP.
- Any laboratory abnormality assessed as clinically significant by the investigator (see Section 11.4.4).

Serious adverse event definition

An SAE is any untoward medical occurrence that

- Results in death.
- Is life-threatening.

- Requires inpatient hospitalisation or prolongation of existing hospitalisation. Planned hospitalisation or planned prolonged hospitalisation do not fulfil the criteria for being an SAE but should be documented in the subject's medical record.
- Results in persistent or significant disability/incapacity.
- Is a congenital anomaly/birth defect.

or

- Is a medically important condition. Events that may not be immediately life-threatening or result in death or hospitalisation but may jeopardise the subject or may require intervention to prevent one of the other outcomes listed in the definition above. Examples are intensive treatment in an emergency room or at home for allergic broncospasm, blood dyscrasias and convulsions that do not result in hospitalisation, development of drug dependency or drug abuse.

Appendix 2: Classification of adverse events

Severity

The *severity* of the AE should be described in terms of mild, moderate or severe according to the investigator's clinical judgement.

Mild	An AE that is usually transient and may require only minimal treatment or therapeutic intervention. The event does not generally interfere with usual activities of daily living.
Moderate	An AE that is usually alleviated with additional specific therapeutic intervention. The event interferes with usual activities of daily living, causing discomfort but poses no significant or permanent risk of harm to the subject.
Severe	An AE that interrupts usual activities of daily living, or significantly affects clinical status, or may require intensive therapeutic intervention.

If the severity of an AE worsens, a new AE should be recorded.

Causality

The *causal relation* of the AE to the use of the IMP should be described in terms of probably, possibly, or not related according to the investigator's clinical judgement. The categories are defined below.

Probably related	
Follows a reasonable temporal sequence from administration of the IMP.
 
Could not be reasonably explained by the subject's clinical state, environmental or toxic factors or other therapies administered to the subject.

	
Follows a known pattern of response to the IMP.
 
Disappears or decreases on cessation or reduction in dose of the IMP.
 
Reappears or worsens upon re-challenge.

Possibly related	
Follows a reasonable temporal sequence from the administration of the IMP.
 
Could also be reasonably explained by the subject's clinical state, environmental or toxic factors or other therapies administered to the subject.
 
Follows a known pattern of response to the IMP.

Not related	
Does not follow a reasonable temporal sequence from administration of the IMP.
 
Is better explained by other factors like the subject's clinical state, environmental or toxic factors or other therapies administered to the subject.
 
Does not reappear or worsen upon re-challenge.
 
Does not follow a known pattern of response to the IMP.

Outcome

The *outcome* of the event according to the investigator's clinical judgement should be classified using the categories below.

Recovered/ resolved	The event has stopped. The stop date of the event must be recorded.
Recovering/ resolving	The subject is clearly recovering from an event. The event is not yet completely resolved.
Not recovered/ not resolved	Event is still ongoing.
Recovered/ resolved with sequelae	
The event has reached a state where no further changes are expected, and the residual symptoms are assumed to persist. An example is hemiparesis after stroke.
 
The stop date of the event must be recorded. In case of a SAE, the sequelae should be specified.

Fatal	The subject has died as a consequence of the event. Date of death is recorded as stop date for the AE.
Unknown	Unknown to investigator, e.g., subject lost to follow-up.

Note that as per the above definition, LEO uses “RECOVERED/RESOLVED” only if an event has actually stopped. According to the CDISC definition, the category “RECOVERED/RESOLVED” also includes events which have improved. However, following the LEO definitions above, such an improved event will instead be classified as “NOT RECOVERED/NOT RESOLVED” or “RECOVERING/RESOLVING”.

Similarly, it should be noted that as per the above definition, LEO uses “RECOVERED/RESOLVED WITH SEQUELAE” only if an event has reached a state where the residual symptoms are assumed to persist. According to CDISC, an event is considered “WITH SEQUELAE”, if it has “retained pathological conditions”. Consequently, it is likely that some of the events classified by LEO with the outcome “RECOVERED/RESOLVED WITH SEQUELAE” could have been classified with the outcome “RECOVERED/RESOLVED” according to the CDISC definition.

For SAEs which have stabilised and cannot be expected to resolve during study or safety follow-up periods, for example chronic illnesses, ‘not resolved’ is accepted as the final outcome and a statement that the SAE has stabilised or is chronic should be added to the narrative in the SAE form.

